9.3 Data collection

The designated investigator staff will enter the data required by the protocol into the Case Report Forms. The CRFs have been built using fully validated secure web-enabled software that conforms to 21 CFR Part 11 requirements, Investigator site staff will not be given access to the EDC system until they have been trained. Automatic validation programs check for data discrepancies in the CRFs and, allow modification or verification of the entered data by the investigator staff.

The Principal Investigator is responsible for assuring that the data entered in the CRF is complete, accurate, and that entry and updates are performed in a timely manner.

Pharmacokinetic (PK) [REDACTED] (blood) samples drawn during the course of the study will be collected from the investigator sites and analyzed by Novartis or a central laboratory contracted by Novartis. The site staff designated by the investigator will enter the information required by the protocol onto the PK [REDACTED] Sample Collection CRFs, as well as onto the designated CRO's requisition form. One copy of the requisition form will be sent to the CRO with the relevant information (including study number, patient ID, etc.) and one copy will be retained by the site.

IRT, ECG tracings and Imaging (MRI and DXA) will be transferred to central readers. Method for data collection will be described in respective manuals. A [Laboratory Manual] will also be available for Central laboratory.

9.4 Database management and quality control

Novartis personnel (or designated CRO) will review the data entered by investigational staff for completeness and accuracy. Electronic data queries stating the nature of the problem and requesting clarification will be created for discrepancies and missing values and sent to the investigational site via the EDC system. Designated investigator site staffs are required to respond promptly to queries and to make any necessary changes to the data.

Concomitant treatments and prior medications entered into the database will be coded using the WHO Drug Reference List, which employs the Anatomical Therapeutic Chemical classification system. Medical history/current medical conditions and adverse events will be coded using the Medical dictionary for regulatory activities (MedDRA) terminology.

Laboratory samples for hematology, biochemistry, coagulation, thyroid panel, serum pregnancy test and others assessments (Testosterone, estradiol, Plasma ACTH, cortisol, 11-deoxycortisol Plasma and serum aldosterone, ██████████, Plasma 11-Deoxycorticosterone, Fasting Insulin and plasma glucose, HbA1C, Serum Androstenedione, DHEAS, Estrone) will be performed by a Central Laboratory. Results of analysis tested centrally will be reconciled and sent electronically to Novartis (or a designated CRO). Unscheduled laboratory analysis performed locally will be collected directly in CRF by the sites.

Samples and/or data for ██████████ PK sampling, imaging and IRT will be processed centrally and the results will be sent electronically to Novartis (or a designated CRO).

Randomization codes and data about all study treatments dispensed to the patient and all IRT assigned dosage changes will be tracked using an Interactive Response Technology. The system will be supplied by a vendor(s), who will also manage the database. The data will be sent electronically to Novartis personnel (or designated CRO).

At the conclusion of the core study, the occurrence of any emergency code breaks will be determined after return of all code break reports and unused drug supplies to Novartis personnel (or designated CRO). The occurrence of any protocol violations will be determined. After these actions have been completed and the data has been verified to be complete and accurate, the database will be declared locked and the treatment codes will be unblinded and made available for data analysis. Authorization is required prior to making any database changes to locked data, by joint written agreement between the Global Head of Biostatistics and Data Management and the Global Head of Clinical Development.

For EDC studies, after database lock, the investigator will receive a CD-ROM or paper copies of the patient data for archiving at the investigational site.

10 Statistical methods and data analysis

The primary analysis will be performed based on cumulative data collected up to the date when all enrolled patients have either completed or prematurely withdrawn from the core phase of study. The results and outcomes of this analysis will be presented in a CSR. All additional data collected subsequently to the cutoff date for the primary analysis will be included in the analysis for the final CSR, which will be performed once all patients have either completed the extension

phase or discontinued earlier. Additional database lock/analysis could be performed after the primary analysis to support the publication of manuscripts.

Novartis or designated CRO will analyze all data using the Statistical Analysis System (SAS) for data analysis V9.3 or higher. Any data analyses carried out independently by an investigator should be submitted to Novartis before publication or presentation.

The data from all centers participating in the trial will be combined, so that an adequate number of patients will be available for analysis. The statistical analysis methods described in this section will focus on the analysis of the data in the core study. Similar methods will be applied to the analyses in the extension phase as appropriate.

10.1 Analysis sets

10.1.1 Randomized Analysis Set

The Randomized Analysis Set (RAS) comprises all randomized patients who have received at least one dose of randomized drug (LCI699 or placebo). According to the ITT principle, patients will be analyzed according to the treatment and stratum they have been assigned to during the randomization.

10.1.2 Full Analysis Set

The Full Analysis Set (FAS) comprises all enrolled patients who receive at least one dose of LCI99. This is the default analysis set for efficacy.

10.1.3 Safety set

There are two safety sets defined in this study:

Safety Analysis Set (SAS) includes all patients who received at least one dose of LCI699 and had at least one valid post-baseline safety assessment.

Safety Analysis Set for randomized withdrawal period (SASR) includes only randomized patients who received at least one dose of randomized treatment (LCI699 or placebo) and had at least one valid safety assessment during the randomized withdrawal period.

Please note: the statement that a patient had no adverse events (on the Adverse Event CRF) constitutes a safety assessment.

For safety analysis, patients will be analyzed according to the study treatment received, where treatment received is defined as the randomized/assigned treatment if the patient took at least one dose of that treatment or the first treatment (first dose of the study for SAS and first dose of randomized withdrawal period for SASR) received if the randomized/assigned treatment was never received.

10.1.4 Per-Protocol set

There are two per-protocol sets defined in this study:

Per-Protocol Set for Randomized Analysis Set (PPRAS) consists of a subset of the patients in the RAS who are compliant with the requirements of the Clinical Study Protocol (CSP) and have no selected CSR-reportable protocol deviations.

Per-Protocol Set for Full Analysis Set (PPFAS) consists of a subset of the patients in the FAS who are compliant with the requirements of the CSP and have no selected CSR-reportable protocol deviations.

The details of selected CSR-reportable protocol deviations will be provided in the SAP.

10.1.5 Pharmacokinetic analysis set

The pharmacokinetic analysis set (PAS) consists of all patients who receive at least one dose of LCI699 and have at least one evaluable pharmacokinetic concentration (post-first-dose) at any visit.

Additional definition of an evaluable PK blood sample will be further specified in the SAP.

10.1.6 Other analysis sets

Not Applicable.

10.1.6.1 Efficacy/evaluable set

Not Applicable.

10.2 Patient demographics/other baseline characteristics

Demographic and other baseline data will be summarized descriptively for the FAS and RAS.

Categorical data will be presented as frequencies and percentages. For continuous data, mean, standard deviation, median, 25th and 75th percentiles, minimum, and maximum will be presented.

Relevant medical histories and current medical conditions at baseline will be summarized by system organ class and preferred term, by treatment group using FAS and RAS.

10.3 Treatments (study treatment, concomitant therapies, compliance)

When appropriate, patients in a given analysis set can be classified into mutually exclusive treatment groups as described below:

For patients in RAS/PPRAS

- LCI699 group: patients randomized to continued treatment of LCI699 for the randomized withdrawal period of the study
- Placebo group: patients randomized to placebo for the randomized withdrawal period of the study

For patients in FAS/PPFAS

- LCI699 group: patients randomized to continued treatment of LCI699 for the randomized withdrawal period of the study

- Placebo group: patients randomized to placebo for the randomized withdrawal period of the study
- Non-randomized patients: patients who do not enter randomized withdrawal period of the study

For patients in SAS

- LCI699 group: patients receiving continued treatment of LCI699 for the randomized withdrawal period of the study
- Placebo group: patients receiving placebo for the randomized withdrawal period of the study
- Non-randomized patients: patients who do not enter randomized withdrawal period of the study

For patients in SASR

- LCI699 group: patients receiving continued treatment of LCI699 for the randomized withdrawal period of the study
- Placebo group: patients receiving placebo for the randomized withdrawal period of the study

The Safety set will be used for the analyses below. Categorical data will be summarized as frequencies and percentages. For continuous data, mean, standard deviation, median, 25th and 75th percentiles, minimum, and maximum will be presented.

The duration of exposure (Week) to study drugs will be summarized by means of descriptive statistics.

The number of patients with dose reductions, interruption, or permanent discontinuation and the reasons will be listed and summarized by treatment arms, and all dosing data will be listed. Concomitant medications and significant non-drug therapies prior to and after the start of the study treatment will be listed and summarized according to the Anatomical Therapeutic Chemical (ATC) classification system, preferred term and treatment groups. The doses and dosing frequency of concomitant medications for the treatment of hypertension, diabetes, and dyslipidemia captured on the concomitant medication CRF, will be taken into account in the analysis of safety and efficacy.

10.4 Primary objective

The primary objective is to compare the complete response rates at the end of the 8 weeks period of randomized withdrawal (Week 34) between patients randomized to continued LCI699 therapy vs. placebo.

10.4.1 Variable

The primary efficacy variable is the proportion of randomized patients in each treatment arm that are complete responders at the end of the 8 weeks of the randomized withdrawal period (Week 34). A complete responder is defined as a patient who has $mUFC \leq ULN$ (based on central laboratory result) at Week 34 and was neither discontinued nor had LCI699 dose increase above the level at week 26 during the randomized withdrawal period of the study.

Patients who discontinued during the randomized withdrawal period will be counted as non-responders for the primary endpoint. Dose reductions and temporary dose interruptions for safety reason during randomized withdrawal period do not preclude patients from being complete responder for primary endpoint.

10.4.2 Statistical hypothesis, model, and method of analysis

For the primary objective, the statistical null hypothesis states that the complete response rates at the end of 8-week randomized withdrawal period (i.e., at Week 34) are the same between the two randomized arms. To test this hypothesis, a Cochran–Mantel–Haenszel exact test stratified by the two stratification factors considered for randomization will be performed using the RAS following the intent-to-treat principle.

If the 2-sided p-value is ≤ 0.05 and the odds ratio (LCI699 vs. Placebo) is > 1 , the null hypothesis will be rejected and the complete response rate in the LCI699 arm will be considered higher than that in the placebo arm.

10.4.3 Handling of missing values/censoring/discontinuations

The mUFC will be determined at a central laboratory from three 24-hour urine specimens collected within 7 days from scheduled visit date. The mean of the results from the 3 samples will be used to obtain the corresponding mUFC level for a given assessment. If a patient has two or more missing UFC values for a particular visit, the mUFC assessment for that patient at that visit will be considered missing. Otherwise, the mean of UFC collections will be considered as the mUFC level for that visit.

Randomized patients who discontinued during the randomized withdrawal period or had a missing mUFC assessment at end of the randomized withdrawal period (Week 34) will be counted as non-responders for the primary endpoint.

10.4.4 Supportive and sensitivity analyses

As a supportive analysis to the primary analysis, an un-stratified Fisher's exact test of the primary endpoint will be performed using RAS.

In addition, both stratified CMH exact test and un-stratified Fisher's exact test of the primary endpoint will be performed using PPRAS.

10.5 Secondary objectives

10.5.1 Key secondary objective(s)

The key secondary objective is to assess the complete response rate (proportion of enrolled patients with $mUFC \leq ULN$) at the end of 24 weeks of dose-titration and treatment with LCI699 in the initial single-arm, open label part of this trial.

The key secondary efficacy variable is the proportion of complete responders at Week 24. A complete responder is defined as an enrolled patient who has $mUFC \leq ULN$ at Week 24 and the dose of LCI699 during Study Period 2 (Weeks 13-24) was not increased above the level established at the end of Study Period 1 (Week 12).

Dose reductions and temporary dose interruptions for safety reasons do not preclude patients from being complete responder for the key secondary endpoint.

Enrolled patients who had missing mUFC assessment at Week 24 will be counted as non-responders for the key secondary endpoint.

For the key secondary objective, the statistical null hypothesis states that the complete response rate at the end of 24 weeks open label period of LCI699 treatment is $\leq 30\%$. The analysis of the key secondary objective will be based on the 2-sided 95% exact confidence interval (Clopper-Pearson method). If the lower bound of this 95% confidence interval is $\geq 30\%$, the null hypothesis will be rejected and the complete response rate will be considered at least 30% after 24 weeks of treatment with LCI699.

The above testing on the key secondary objective will only be carried out if the null hypothesis for the primary objective is rejected. This sequential procedure will ensure preservation of the overall 2-sided type 1 error at 5%.

The primary analysis of the key secondary endpoint will be performed using FAS. An additional analysis will be performed using PPFAS.

10.5.2 Other secondary efficacy objectives

10.5.2.1 Compare the time-to-last control of mUFC during the randomized withdrawal period between patients randomized to continued LCI699 and placebo

Time-to-last control of mUFC during the randomized withdrawal period will be analyzed using K-M plot and stratified logrank test. Time-to-last control of mUFC is defined as the time (in days) from randomization to the time of the last normal UFC assessment ($mUFC \leq ULN$ based on central laboratory result) before early discontinuation or completion of randomized withdrawal period, whichever is earlier. RAS will be used for this analysis.

10.5.2.2 Assess the complete, partial, and overall response rate at Week 12, Week 24, Week 48, and during the extension period

Proportion of complete responder (enrolled patients with $mUFC \leq ULN$), partial responder (enrolled patients with $mUFC > ULN$ and at least 50% reduction from baseline), and overall responder (enrolled patients with $mUFC \leq ULN$ or have at least 50% reduction from baseline) at Week 12 (end of period 1), Week 24 (end of period 2) and Week 48 (end of period 4) as well as at scheduled time points during the extension period (provided adequate follow-up as specified in the SAP) and the last available assessment will be summarized using point estimates and 95% CIs.

10.5.2.3 Assess the change in mUFC during the core and extension period of the study

For the actual and percentage change in mUFC from baseline, descriptive summaries will be provided for every visit in core and extension (provided adequate follow-up as specified in the SAP) at which UFC is collected. 95% CIs for the percentage change from baseline will also be provided.

For the actual and percentage change in mUFC from the randomization (Week 26) to the end of randomized withdrawal period, or the last mUFC measurement prior to early discontinuation, whichever occurs earlier, in addition to the descriptive summaries, the difference between two randomized arm and associated 95% C.I. will be estimated with adjustment for mUFC at randomization. RAS will be used for the analysis.

10.5.2.4 Assess the change in cardiovascular-related metabolic parameters associated with Cushing's disease during the core and extension period of the study

For cardiovascular-related metabolic parameters associated with Cushing's disease (e.g. fasting glucose, HbA1c, fasting lipid profile, SBP, DBP, weight, waist circumference and BMI):

For actual and percentage change from baseline during the core and extension period (provided adequate follow-up as specified in the SAP) of the study, descriptive summaries will be provided.

For the actual and percentage change from the randomization (Week 26) to the end of randomized withdrawal period, or the last measurement available prior to early discontinuation, whichever occurs earlier, in addition to the descriptive summary, the difference between two randomized arm and associated 95% C.I. will be estimated with adjustment for corresponding parameter value at randomization. RAS will be used for the analysis.

10.5.2.5 Assess the change from baseline in physical features of Cushing's disease by photography

For each of physical features of Cushing's disease: facial rubor, hirsutism, striae, supraclavicular fat pad, dorsal fat pad, proximal muscle wasting (atrophy), central (abdominal) obesity, and ecchymoses (bruises). The change from baseline at Week 12, 24, 34 and 48 as well as during the extension at Week 72 and EOT extension will be assessed using shift table.

10.5.2.6 Assess the change from baseline in bone mineral density by DXA scan at Week 48 and the last available assessment

For bone mineral density measured by DXA scan at the lumbar spine and total hip, descriptive summaries of actual and percentage change from baseline at Week 48 and the last available assessment will be provided.

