A Steering Committee has been established; see [Section 8.7](#) for additional detail. A Novartis Safety Management Team (SMT) exists to review and evaluate all emerging safety data for potential new safety signals on a regular basis and to evaluate safety management across the program.

Conclusion

Based on current data, and the planned risk mitigation processes, the overall benefit-risk of trial participation is expected to be positive for all trial subjects, including those randomized to placebo during the randomized withdrawal period.

3 Objectives and endpoints

[figure not shown]
Objectives and related endpoints are described in [Table 3-1](#) below.

Table 3-1 Objectives and related endpoints

Objective	Endpoint	Analysis
Primary		
To compare the complete response rate at the end of the 8-week period of randomized withdrawal (Week 34) between patients randomized to continued LCI699 therapy vs. placebo.	Proportion of randomized patients in each arm with: mUFC \leq ULN at the end of 8 weeks of randomized withdrawal (Week 34), and were neither discontinued, nor had LCI699 dose increase above the level at week 26 during the randomized withdrawal period.	Refer to Section 10.4.
Key secondary		
To assess the complete response rate at the end of individual dose-titration and treatment with LCI699 in the initial single-arm, open label period (Week 24).	Proportion of enrolled patients with mUFC \leq ULN at Week 24 and had no dose increase above the level established at Week 12 between Week 13 and Week 24.	Refer to Section 10.5.1.
Other secondary		
To compare the time-to-last control of mUFC during the randomized withdrawal period between patients randomized to continued LCI699 therapy and placebo.	Time-to-last control of mUFC, which is defined as the time (in days) from randomization to the last mUFC collection that was \leq ULN before early discontinuation or completion of randomized withdrawal period, whichever is earlier.	Refer to Section 10.5.2.

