4.1.3.4 UFC monitoring during randomized withdrawal

During the 8-week randomized withdrawal study period, mUFC is measured at scheduled visits every 2 weeks. However, patients are also allowed to have unscheduled visits at any time during the randomized withdrawal period if they report symptoms of hypercortisolism or hypocortisolism. The investigator decides the dose of study drug (LCI699 or placebo) during this period, although is blinded to treatment assignment. All laboratory tests during the randomized withdrawal period must be sent to the central laboratory for analysis, and all treatment decisions must be based on central laboratory results.

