4.1.3.6 Discontinuation from randomized withdrawal

During the randomized withdrawal study period, the patient must be discontinued from the randomized withdrawal period, declared a non-responder, if the mUFC increases to $> 1.5 \times$ ULN, and at least 2 individual urine samples show UFC $> 1.5 \times$ ULN at a single visit (scheduled or unscheduled).

After discontinuation from randomized withdrawal, or at the end of the randomized withdrawal period (Week 34), whichever comes first, the patient resumes open-label LCI699 at a dose selected by the investigator.

Patients who are discontinued from the study for reasons other than those described above during the randomized withdrawal period are no longer in the study, and consequently they are not permitted to receive open-label LCI699 and cannot move forward to Study Period 4.

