10.5.2.7 Assess the time-to-escape under treatment of LCI699

Escape is defined as the first loss of control of UFC that meets all of the following criteria:

- prior normalization of mUFC has occurred ($mUFC \leq ULN$)
- both the mean UFC and at least 2 individual values contributing to that mUFC have to be $>1.5 \times ULN$
- the loss of control of UFC is not related to a dose interruption or dose reduction due to safety reasons
- happens beyond 12-week dose titration period (Study Period 1).

For patients who attained normal mUFC (\leq ULN), time-to-escape will be analyzed using K-M plot. Time-to-escape is defined as the time (in days) between the first UFC assessment with $mUFC \leq ULN$ and either the UFC assessment of escape (event) or last UFC assessment before discontinuation of LCI699 treatment (censored), whichever occurs earlier.

Patients randomized to placebo are not included in this analysis.

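### Time-to-last control is analysed by Kaplan-Meier and logrank with no stated event or censoring status, and the last normal value does not track loss of control

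*Protocol*

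**What the plan says.** Protocol 10.5.2.1 names the method: "Time-to-last control of mUFC during the randomized withdrawal period will be analyzed using K-M plot and stratified logrank test". It defines the variable: "Time-to-last control of mUFC is defined as the time (in days) from randomization to the time of the last normal UFC assessment", with the window closing "before early discontinuation or completion of randomized withdrawal period, whichever is earlier". The analysis set is the RAS. Table 3-1 of the protocol has the same definition ("the time (in days) from randomization to the last mUFC collection that was" at or below ULN), as do the protocol summary and SAP Table 1-1. None of these places gives an event or a censored status.

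The other time-to-event endpoint does. Protocol 10.5.2.7, time-to-escape, labels the escape assessment as the event, "or last UFC assessment before discontinuation of LCI699 treatment (censored), whichever occurs earlier". SAP 2.7.7 repeats those labels.

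Three design features bear on the point:

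- Protocol 4.1.3.4: "During the 8-week randomized withdrawal study period, mUFC is measured at scheduled visits every 2 weeks".
- Protocol 4.1.3.6: "the patient must be discontinued from the randomized withdrawal period, declared a non-responder, if the mUFC increases to" above 1.5 x ULN and at least two individual samples at one visit exceed the same limit.
- Protocol 4.1.3.6, on other exits: "Patients who are discontinued from the study for reasons other than those described above during the randomized withdrawal period are no longer in the study".

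SAP 2.7.1 says only that the interim CSR reported this objective and that it will not be repeated. SAP section 1 refers to a core-phase SAP with cover date 06-Jul-2018. SAP 1.2.3 dates unblinding to 10-May-2018.

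**The concern.** A Kaplan-Meier curve needs two things: an event that can be recognised when it happens, and a rule for patients who have not had it. Here the first is doubtful and the second is not stated.

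Every patient with any normal value after randomization has a last normal date, including one still controlled at Week 34. Whether the Week 28 value is the last normal one depends on Weeks 30 to 34, so the usual at-risk reading of the curve does not apply. A patient who is above ULN in mid-period, is not removed, and is normal again at Week 34 gets the same time as one who was never above ULN. A patient who leaves for an unrelated reason while controlled is timed at the last normal value, and nothing separates that exit from a loss of control.

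At stake is a time-to-event comparison of the randomized arms in a withdrawal design, where the timing of loss of control is of direct interest. Time-to-escape cannot fill this role, because it excludes placebo patients.

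**Working it through.** **Plan's own figure.** The documents give no sample size, event count or power for this endpoint. The anchor is the primary calculation (protocol 10.8): 70% vs 30%, 33 per arm, two-sided 0.05, 87% power. With a continuity correction:

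- Null SE = sqrt(2 x 0.5 x 0.5 / 33) = 0.1231.
- Alternative SE = sqrt((0.7 x 0.3 + 0.3 x 0.7) / 33) = 0.1128.
- z = (0.40 - 1/33 - 1.96 x 0.1231) / 0.1128 = 1.14, so power is 87.3%.
- Enrolment = 66 / 0.5 = 132.

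The stated figures reproduce.

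**What follows from the definition alone.**

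1. *Lapses.* Compare two patients at Weeks 28, 30, 32 and 34: (normal, high, high, normal), with the high values not meeting the exit rule, and (normal, normal, normal, normal). Both score day 56. Time to first mUFC above ULN is day 28 for the former, and the latter is censored at day 56.
2. *Looking ahead.* For the former patient, whether day 14 is the last normal date is unknown until Week 34 is read.
3. *Time zero or less.* Protocol 7.2.1.1 has urine collected within the 7 days before a visit. SAP 2.1.1.5 dates an mUFC by its last sample. A patient with no normal value after randomization has either no time or, if the Week 26 value counts, a time that can be zero or negative. No handling is given.

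**Effect of the missing rule (simulation, rates assumed).** There were 33 patients per arm, visits at days 14, 28, 42 and 56, and 4,000 runs with an unstratified logrank test. Assumed per-visit probabilities, LCI699 / placebo:

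- normal to lapse: 8% / 17%
- normal to removal: 2.7% / 16.5%
- lapse back to normal: 38% / 30%
- drop-out for other reasons: 1.5% / 1%

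A lapsed patient could also be removed. The rates were tuned to about 71% and 30% normal at Week 34. As a check on the first-loss curve: (1 - 0.08 - 0.027)^4 = 0.893^4 = 64%, and (1 - 0.17 - 0.165)^4 = 0.665^4 = 20%.

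K-M estimate at Week 34, same data:

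| Rule | LCI699 | Placebo |
|---|---|---|
| Every last normal value is an event | 0% | 0% |
| Week 34 normals censored | 71% | 30% |
| Non-efficacy drop-outs also censored | 75% | 31% |
| Only patients removed under 1.5 x ULN are events | 89% | 43% |
| Time to first mUFC above ULN | 64% | 20% |

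*Lapses.* About 11% of each arm lapsed and still scored about day 56. As a share of those normal at Week 34, that is 0.108 / 0.709 = 15% on LCI699 and 0.107 / 0.295 = 36% on placebo. A second simulation used log-normal mUFC (assumed log SD 0.5-0.6 between and 0.3-0.4 within patients). It gave 14-23% and 29-40%, but it ended follow-up on the mean alone and left out the two-sample condition.

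*Time zero.* In the first simulation 1 - 0.935 = 6.5% of LCI699 and 1 - 0.743 = 25.7% of placebo patients had time zero. In the second the figures were 7-16% and about 40%.

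*Power.* On exact visit days it was 95% whether Week 34 normals were events or censored, against 97% for first loss. With the visit window of 3 days either side (protocol 7.1.3), counting them as events lowered power to 79%, because visit-date noise then ranks the completers. Censoring them kept it at 95%.

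*Unequal drop-out.* Efficacy was set equal, and non-efficacy drop-out was assumed at 6% vs 1% per visit. With drop-outs as events and Week 34 normals censored, the test rejected in 20-21% of trials. With Week 34 normals also events and the visit window applied, it rejected in 13%. With drop-outs censored it rejected in about 5%, and with first loss in about 6%.

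**The case against.** The strongest reply is that the material supports a drafting gap and little more. Most of its parts have force.

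- *The core-phase SAP may hold a censoring rule.* This stands. A reader might infer that no rule exists anywhere, but the documents show only that none is in the protocol or the supplied SAP. The cited cover date follows unblinding, so a rule found only there could not be shown from these documents to be prespecified. Nor would it cure the looking ahead or the lapses.
- *That all patients are events and both curves fall to zero is one reading.* This stands. Censoring patients normal at completion is equally open, and it gives 71% vs 30%, in line with the planned response rates.
- *The curve is not meaningless and does not conceal early failure.* This stands. The arms already separate at time zero, logrank power is good, and SAP 2.3.1 tabulates discontinuation from randomized treatment by arm at each two-week step.
- *Ignoring lapses is a choice of endpoint.* This stands in part. The primary endpoint also accepts a patient who lapsed and is normal at Week 34, and it also counts discontinuations as failures. But that endpoint describes status at one visit, whereas a time-to-event curve is read as the course of control.
- *First mUFC above ULN is stricter than the protocol's own threshold.* This stands, and is a reason to show the removal criterion beside it.
- *That this is the only time-to-event comparison of the arms cannot be confirmed.* This stands. It is the only one visible, but part of the protocol's analysis section is redacted.

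**Conclusion.** The point holds in a limited form. On the supplied documents, event and censoring status is unstated for an endpoint analysed by K-M and logrank. The last-normal definition also depends on later visits and leaves out lapses below the exit rule, whatever censoring is used. Leaving while controlled counts as loss of control unless such exits are censored.

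If Week 34 normals are censored and lapses are rare, the curve is close to a loss-of-control curve shifted about one visit early. A reader might go further and conclude that the reported comparison has no meaning or that the trial's efficacy result is in doubt. The documents support neither. This endpoint lies outside the testing sequence, so the primary and key secondary tests are untouched.

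The directions of effect follow from the definition. The sizes rest on assumed transition rates, variability and drop-out, none of which the documents give.

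**What to change.** State the status of each type of patient for time-to-last control:

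- normal at Week 34: censored
- removed under the 1.5 x ULN rule: event
- leaving for another reason while controlled: censored at the last assessment
- never normal after randomization: event at the first post-randomization assessment

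The text should also say what happens to a patient who is above ULN at the last assessment without having been removed.

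Add two analyses in the RAS, labelled supplementary, with the same stratified logrank test and K-M plot: time from randomization to first mUFC above ULN, and time to the protocol's existing removal criterion (mUFC and at least two samples above 1.5 x ULN). Keep the reported endpoint; these stand beside it.

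The cost is one extra derivation on two-weekly data already collected. The additions would be post hoc, because the study is unblinded and the interim CSR has reported the endpoint. SAP 2.1 also rules out formal testing in the Final CSR, so any p-value there would be descriptive. First mUFC above ULN reacts to single small fluctuations, which is why the removal criterion is shown with it.
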